## 2.3 Procedures

Baseline (within 1 week prior to Dysport® treatment):

Before initiating any study procedures the informed consent will be discussed and signed with the parent(s) of the participants and the researcher will answer any questions. If capable of providing assent (>7 years old), the participant will sign the assent form. Once the consent and assent forms are discussed and signed the following assessments will be performed: demographics, height, weight, calculated body mass index (BMI), Modified Ashworth Scale (MAS), modified Tardieu Scale, range of motion of major joints (i.e., hip, knee, ankle), the Cerebral Palsy Quality of Life Questionnaire (CP QOL) for Children (9-12 years) or Adolescents (13-18 years), and the CP QOL for caregivers, 6 minute walk test (with mobile oxygen consumption), and gait analysis.

Degree of spasticity/tone in the lower limbs will be measured by the Modified Ashworth scale while the participant is relaxed and in the supine position (1). If testing a muscle that primarily flexes the hip, knee, or ankle joint the investigator will place the joint in a maximally flexed position and move the joint to a position of maximal extension over one second. If testing a muscle that primarily extends the hip, knee, or ankle joint the investigator will place the

joint in a maximally extended position and move the joint to a position of maximal flexion over one second.

The Modified Tardieu Scale will be used to assess spasticity by measuring different angles of muscle reaction in response to a passive force (2). Two angles will be measured from each major joint (i.e., hip, knee, ankle): R1, the angle in which clonus was felt during a quick passive stretch of the muscle; R2, the angle of full passive range of motion. The difference between the two angles ( $R2 - R1$ ) will be recorded for each muscle group. The participant will be lying supine for all angle measurements.

Range of motion of the lower limbs (hip, knee, ankle) will be measured by passively moving the patient's joint to a point of resistance where then the joint angle will be measured by a goniometer. Hip flexion will be measured with the patient lying supine. Knee flexion and extension will be measured with the patient lying supine. Ankle dorsiflexion will be measured with the knee extended in the supine position. The Thomas Test will also be used to assess hip flexion with the patient lying in supine (3).

The CP QOL for children, adolescents, and caregivers will be used to assess quality of life and wellbeing across multiple domains of life (4). For children 4-12 years, we will give the primary caregiver version to their parent or guardian. For children 9-12 years, we will give the child self-report version. For adolescents 13-18 years, we will give the teen self-report version as well as the primary caregiver version to their parents or guardian. The sum for each domain will be calculated as well as the total sum.

Gait analysis and the 6 Minute Walk Test (6MWT) with oxygen consumption measurement (energy expenditure) will be performed in the Department of Rehab by an exercise physiologist. Children will be given at least a ten minute rest between measures.

Gait analysis will be measured with the GAITRite® mat, a commercially available instrumented mat for collection of gait data. The GAITRite system is an electronic walkway that connects to a computer, and automates the measurement of temporal (timing) and spatial (distance) gait parameters, such as cadence, step length and velocity. The standard GAITRite walkway is (5m long) and contains 13824 sensors encapsulated in a roll up mat to produce an active area 0.6 m wide and 4.25 m long. The walkway is portable, can be laid over any flat surface and requires no placement of any devices on the patient. GAITRite uses no radiation, electricity or ultrasound to measure these parameters and is therefore a safe method for evaluating walking function, even during pregnancy. The system has been validated for use in healthy children and children with movement disorders (such as cerebral palsy, and spinal muscular atrophy) (5, 6). The laboratory consists of a 10-meter walkway. The GAITRite mat is placed in the middle of the 10 meter walkway to collect data on steady state gait without the influence of gait initiation and termination. Subjects will be asked to wear the same shoes and orthoses throughout the study. A gait aid can be used during the test if the child cannot walk without it. Subjects will be asked to begin walking at a starting position located 1.5 meters from the mat and walk at their preferred typical speed until a termination position marked on the floor (1.5m from the end of the mat). Each subject will perform five trials of walking at their preferred speed. We will compute gait

velocity, step length, cadence, percent time spent in double support, foot angle, and base of support.

After at least a ten minute rest, oxygen consumption via the breath-by-breath method using a portable spirometric device (Cosmed K5; COSMED USA Inc, Concord, CA) will be determined while the participant performs the 6MWT (7). After instruction the participant will don the face mask and a 12 lead ECG will be applied. In order for the child to become comfortable with the face mask, a three minute rest period will be given while resting heart rate (HR) and oxygen consumption (VO2) is measured. After the three minute rest, the participant will begin the 6MWT while the K5 mobile device collects gas exchange variables [VO2, VCO2, respiratory exchange ratio (RER)] and HR will be monitored via the 12-lead ECG as well as cardiac rhythm. Participants will be instructed to walk at their normal walking pace as far as they can for six minutes. They will be allowed to walk with any orthoses and/or assistive devices however the same orthoses and/or devices will be used throughout the study. The participant can stop at any time if they feel dizzy or fatigued to the point of increased risk of falling. The total distance walked (meters) will be recorded at six minutes.

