### *Subject Visits:*

- **Baseline:** Consent, Modified Ashworth Scale, modified Tardieu Scale, CP Quality of Life Questionnaire for Children/Adolescents, 6 minute walk with VO2 and gait analysis
- **Treatment:** SEMLC treatment

- **4 week follow-up:** Modified Ashworth Scale, modified Tardieu Scale, CP Quality of Life Questionnaire for Children/Adolescents, 6 minute walk with VO2 and gait analysis
- **12 week follow-up:** Modified Ashworth Scale, modified Tardieu Scale, CP Quality of Life Questionnaire for Children/Adolescents, 6 minute walk with VO2 and gait analysis

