## 2.1 Participants

All subjects will be recruited from [name] Physical Medicine & Rehabilitation clinic. [name] will approach eligible patients and their parents in order to explain the study and to determine interest. A researcher of the study team will email and/or telephone call eligible participants on behalf of [name] and with her permission to inform the parents of the eligible participant of the study.

Inclusion Criteria:

- Age: 5-17 years. *Must be <18 prior to injection.*
- >10 kilograms at screening and injection visits
- Diagnosis of spastic diplegia OR mild- to moderate spastic quadriplegia Cerebral Palsy
- Gross Motor Function Classification System level: I, II, III
- Ability to ambulate independently without aid, equinus gait
- Absent of joint or bone deformities
- Eligible to receive SEMLC
- Cooperative and tolerant to testing procedures during clinic screening
- Presence of spasticity in one or both legs
- Be on a stable dose and regimen if on any prescribed medication/s
- Parent must have signed written informed consent and the Patient Authorization for Use and Release of Health and Research Study Information

Exclusion Criteria:

- Ankle contractures no more than -10 degrees with the knee extended
- Hemiplegia
- Wheelchair dependent
- Received Botulinum toxin within previous 4 months
- Uncontrolled epilepsy or certain types of seizures
- Fracture in the study limb within previous 12 months
- Infection or skin disorder at planned injection site
- Shortness of breath or other respiratory issues
- Uncontrolled clinically significant medical condition
- Received phenol or alcohol block in the study limb within previous 6 months
- Surgery in the study limb within previous 12 months
- Serial casting within previous 12 months
- New physiotherapy and/or orthotic regimen <1 month before study start. (physiotherapy and/or orthotic regimen will be permitted if it began >1 month before study start and maintained throughout study)

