## 2.2 Outcome Measures

Primary Question: Does single event multi level chemoneurolysis (SEMLC) have an effect on energy expenditure and walking efficiency as measured by oxygen consumption (VO2) and gait parameters during the 6 minute walk test in 15 children diagnosed with cerebral palsy (CP)?

Hypothesis: If 15 children receive SEMLC, then energy expenditure (VO2) will decrease due to increased walking efficiency and gait parameters during the 6 minute walk test.

Secondary Question: Does SEMLC have an effect on 6 minute walking distance in 15 children diagnosed with CP?

Hypothesis: SEMLC will increase the distance walked during the 6 minute walk test.

Secondary Question: Does SEMLC have an effect on the Gross Motor Functional Classification System (GMFCS) classification in 15 children diagnosed with CP?

Hypothesis: SEMLC will decrease a child's GMFCS classification due to increased physical function.

Secondary Question: Does SEMLC have an effect on ankle muscle spasticity as measured by the Modified Ashworth Scale (MAS) and the modified Tardieu Scale?

Hypothesis: SEMLC will decrease ankle muscle spasticity and in turn improve MAS and modified Tardieu Scale scores.

Secondary Question: Does SEMLC have an effect on dynamic balance during walking in 15 children diagnosed with CP?

Hypothesis: SEMLC will increase dynamic balance during walking.

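### Section 2.3 ties the Tardieu angle R1 to clonus, so a spastic muscle that reacts without clonus has no R1 as written (minor)

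*Combined protocol and SAP*

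**What the plan says.** Section 2.2 asks "Does SEMLC have an effect on ankle muscle spasticity as measured by the Modified Ashworth Scale (MAS) and the modified Tardieu Scale" and predicts that "SEMLC will decrease ankle muscle spasticity and in turn improve MAS and modified Tardieu Scale scores". The scale is therefore one of two measures for one secondary question.

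Section 2.3 says the scale assesses spasticity "by measuring different angles of muscle reaction in response to a passive force". It then defines the two angles for hip, knee and ankle: "R1, the angle in which clonus was felt during a quick passive stretch of the muscle", and "R2, the angle of full passive range of motion". The difference R2 - R1 "will be recorded for each muscle group".

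The visit list in section 2 places "Modified Ashworth Scale, modified Tardieu Scale" at baseline, 4 weeks and 12 weeks. The paragraphs in 2.3 on the two follow-up visits repeat the baseline procedures and add no scoring rule. The relevant inclusion criterion in 2.1 is "Presence of spasticity in one or both legs"; no criterion mentions clonus.

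**The concern.** Clonus is one kind of muscle reaction. By naming it alone, the operational definition covers less than the general description just before it. Every recorded R2 - R1 needs an R1, yet a child can be eligible with spastic muscles that react to quick stretch without clonus. An assessor who follows the printed words has nothing to enter for such a muscle, at baseline or later. The options would be to leave the score blank, to set R1 equal to R2 so that the difference is zero, or to use another reaction as the landmark. The protocol text does not choose among them.

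What is at stake is the completeness and comparability of the Tardieu ankle score in an open-label, single-arm study of 15 children. An angle that is not recorded at a visit cannot be recovered afterwards.

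**Working it through.** **Step 1: the text.** The document gives no Tardieu figure to reproduce, so the first check sets the definition against the possible findings on quick stretch.

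| Finding on quick stretch | R1 if clonus is literal | R1 if clonus means any reaction |
|---|---|---|
| Clonus felt | defined | defined |
| Reaction without clonus | undefined | defined |
| No reaction | undefined | undefined |

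The middle row is the defect in the stated rule: 2.1 admits such muscles and 2.3 requires a value for them. The last row is a missing convention on either reading.

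**Step 2: inputs for an illustration.** From the document: 15 children, visits before and after treatment, and an expected fall in spasticity. Assumed, because the document gives no angle, SD or clonus frequency: one ankle score per child, baseline R2 - R1 with mean 25 and SD 8 degrees, mean change -10 degrees, SD of change 2 to 8 degrees, and values floored at 0. The reaction-based R2 - R1 is taken as the truth. Two conventions are compared by simulation:
- Blank: mean change among children scorable at both visits. Loss = 1 - (blank / true).
- Zero: R2 - R1 set to 0 wherever R1 is undefined. Overstatement = (zero / true) - 1.

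**Step 3: broad reading (only no reaction is undefined).** Dropping blanks makes the estimated change 0.7% too large at SD 2, and 0.1%, about 2% and 5.7% too small at SD 4, 6 and 8. Between 14.5 and 13.6 of 15 pairs remain. Entering R1 = R2 gives no bias, by construction. The effect is small because only 15 - 14.5 = 0.5 to 15 - 13.6 = 1.4 children lack a reaction at one or both visits. A higher frequency could give a larger effect, but the document supports no particular frequency.

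**Step 4: literal reading, clonus felt only above 15 degrees, change independent of baseline.**

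| SD of change | True | Blank | Loss | Zero | Overstated |
|---|---|---|---|---|---|
| 2 | -9.89 | -9.62 | 3% | -13.03 | 32% |
| 4 | -9.83 | -8.58 | 13% | -12.75 | 30% |
| 6 | -9.71 | -7.18 | 26% | -12.33 | 27% |
| 8 | -9.52 | -5.62 | 41% | -11.81 | 24% |

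For example, at SD 8 the loss is 1 - 5.62/9.52 = 41% and the overstatement is 11.81/9.52 - 1 = 24%. About 7.5 of 15 pairs survive dropping.

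**Step 5: how far Step 4 depends on its model.**
- Equal SDs. In Step 4 at SD 8, the follow-up SD before flooring is sqrt(8² + 8²) = 11.3, against 8 at baseline. If instead the SD is 8 at both visits with correlation r, the SD of change is 8 × sqrt(2(1 - r)): 8.0, 6.2 and 3.6 for r = 0.5, 0.7 and 0.9. Blanks then lose 26%, 17% and 6%. The table gives 41%, 26% and 13% at SD 8, 6 and 4. Zeros overstate by 32% throughout.
- Gradual link. If the probability of clonus rises with R2 - R1 along a logistic curve (midpoint 10 to 20 degrees, scale 5 to 20), blanks lose 0 to 2% at SD 2 and 10 to 39% at SD 8. Zeros range from 31% too small to 19% too large.
- No link. If clonus is unrelated to R2 - R1, blanks cause no bias, only fewer pairs. With clonus present in 70% at both visits, zeros give 0.7 × the true change, which is 30% too small.

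On the literal reading, then, neither the size nor the direction is fixed.

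**The case against.** The strongest reply is that clonus is loose shorthand for a catch or any other reaction, so trained assessors would score as usual. That may well be so. On that reading the remaining gap is only the no-reaction case, and Step 3 shows it is small under the assumed inputs. This limits the weight of the point. It does not repair the printed definition, which is the rule an assessor is given.

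Second, 2.3 cites a source for the scale (reference 2), and a scoring convention may be found there. This stands as a limit: the claim is only that the protocol text states no convention. The protocol writes its own R1 and does not say that it defers to that source's scoring.

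Third, this is a single-centre study whose follow-up visits repeat the baseline procedures, and the document does not say that several assessors will score the scale. Inconsistent scoring is therefore a possibility, not something shown. The document also describes no analysis of the Tardieu score, so dropping blanks and counting pairs belong to the illustration, not to the plan.

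A reader might infer that the two sentences in 2.3 contradict each other. They do not: a general description covering both angles is followed by a narrower definition of one. A reader might also infer that children without clonus are to be excluded. Nothing prescribes that; the handling is left open.

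**Conclusion.** The point holds as a minor error in an outcome definition. R1 as written does not cover a spastic muscle that reacts without clonus, although such a muscle is eligible and must be scored. The absence of a convention for no reaction is a lesser matter of missing detail.

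The size is unknown. Under the assumed inputs it is about 1% or less at an SD of change of 2 to 4 degrees and 6% at 8 degrees if clonus means any reaction. If clonus is applied literally, it depends on the model in both size and direction.

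It would be tempting to quote the 41% loss, or to say that the treatment effect will be understated or exaggerated. The document does not support either. The 41% needs literal use of clonus, blanks that are then dropped, a sharp clonus threshold, and a follow-up SD well above baseline; with equal SDs and the same SD of change it is 26%. Entering zeros can err both ways. The VO2 question and the Modified Ashworth Scale are not affected.

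**What to change.** In 2.3, define R1 as the angle of the first muscle reaction, clonus or any other, felt on quick passive stretch, and apply it identically at baseline, 4 and 12 weeks. With that definition in place, state one convention for when no reaction is felt, for example R1 = R2, so that R2 - R1 = 0. The two belong together: a zero entered for every muscle without clonus would score muscles that still react as if they did not. If the intention is to follow the scoring in reference 2, the protocol should say so and restate the rule.

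Recording the presence of clonus separately is optional. The cost is about one sentence, with no added procedure. It should be settled before assessments begin.

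### Mask acclimatisation and resting VO2 share one three-minute window, so first-visit unease may bias the before-after change in VO2, in a direction that depends on whether gross or net VO2 is analysed

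*Combined protocol and SAP*

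**What the plan says.** All the measurement text is in Section 2.3 (Procedures) of the combined protocol and SAP. Gait analysis comes first, then a break: "Children will be given at least a ten minute rest between measures". The oxygen measurement follows: "After at least a ten minute rest, oxygen consumption via the breath-by-breath method" is used during the 6-minute walk test (6MWT). The equipment goes on only at this stage: "After instruction the participant will don the face mask and a 12 lead ECG will be applied".

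The next three minutes have two purposes. One is acclimatisation: "In order for the child to become comfortable with the face mask, a three minute rest period will be given". The other is measurement, because the sentence continues "while resting heart rate (HR) and oxygen consumption" are recorded. Then: "After the three minute rest, the participant will begin the 6MWT while the K5 mobile device collects gas exchange variables".

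There is one baseline visit, within a week before treatment, and the same procedures are repeated at 4 and 12 weeks. Section 2 describes a single-centre, open-label study of 15 children and no control group. Section 2.2 gives the primary hypothesis: "energy expenditure (VO2) will decrease due to increased walking efficiency and gait parameters during the 6 minute walk test". The documents do not say what the resting VO2 is used for, or whether the VO2 endpoint is gross or net of rest.

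**The concern.** The three minutes are meant to let the child settle, so a value averaged over them includes the settling period. A child who is uneasy in a new mask may have a raised heart rate and VO2. The mask is likely to be least familiar at baseline and more familiar at 4 and 12 weeks, so any such excess would be larger before treatment than after it.

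With no control group, a change due to habituation cannot be separated from a change due to treatment. Every child has the same visit order, so no later analysis can recover the difference. The primary hypothesis is a fall in VO2, and an excess at baseline that persists into the walk would produce one. If resting VO2 is subtracted from walking VO2, the same excess acts through the subtracted term and can push the other way. Because the plan does not say which measure is analysed, the direction of the possible bias is unknown.

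**Working it through.** The plan has no figure to reproduce: it states no alpha, test, SD or effect size, and it gives no derivation of the sample size. The check therefore covers direction first, then scale under stated assumptions.

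**Inputs from the documents.** n = 15 (Section 2); a three-minute combined window and a rest of at least ten minutes before it (Section 2.3); hypothesised direction a decrease in VO2 during the walk (Section 2.2).

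**Assumed inputs.** Two-sided 5% paired t-test; no true treatment effect; no unease left at follow-up; resting excess at baseline *b* = 0.5 to 1.5 mL/kg/min; SD of within-child change 2 to 3 mL/kg/min; a share *c* (0 to 1) of the resting excess carries into the walk.

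**Step 1: direction.** Let true resting and walking VO2 be R and W at every visit. Baseline readings are R + b and W + cb; follow-up readings are R and W.

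- Spurious gross change = W − (W + cb) = −cb.
- Spurious net change = (W − R) − [(W + cb) − (R + b)] = (1 − c)b.

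For b = 1 mL/kg/min:

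| Carry-over c | Gross change | Net change |
|---|---|---|
| 0 | 0 | +1 |
| 0.5 | −0.5 | +0.5 |
| 1 | −1 | 0 |

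Gross VO2 is either unaffected or biased towards benefit. Net VO2 is either unaffected or biased against benefit.

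**Step 2: scale for gross VO2.** Let d be the spurious fall in the analysed VO2 divided by the SD of the within-child change. The test statistic is then noncentral t with 14 df and noncentrality d√15 = 3.873d. The chance of a significant decrease is the probability of exceeding the critical value of 2.145 in the favourable direction.

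| d | d√15 | Chance of a false decrease |
|---|---|---|
| 0 | 0 | 2.5% |
| 0.1 | 0.387 | 5.5% |
| 0.2 | 0.775 | 10.8% |
| 0.3 | 1.162 | 19.0% |
| 0.5 | 1.936 | 43.8% |

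A worked link between the two steps: b = 1, c = 0.5 and an SD of 2.5 (the middle of the assumed range) give d = 0.5/2.5 = 0.2, hence 10.8%.

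With complete carry-over, the assumed ranges give d from 0.5/3 = 0.17 to 1.5/2 = 0.75, and a chance of 9% to 77%. With no carry-over, d = 0 and the chance stays at 2.5%.

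**Step 3: scale for net VO2.** Fifteen children give 80% power for a true change of 0.778 SD. If the net measure carries an opposing shift of 0.178 SD, the apparent change is 0.778 − 0.178 = 0.6 SD, for which power is 58%.

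**The case against.** The strongest reply is that the three minutes produce resting VO2, whereas the primary outcome is VO2 during the walk. For the walk, the three minutes are themselves an acclimatisation period. This stands, and it limits the point: gross walking VO2 is affected only if unease persists once the child is walking, and the documents neither show nor exclude that.

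Section 2.1 also requires children to be cooperative with, and tolerant of, the testing procedures at clinic screening. The mask is not named there, but it may have been tried. It is therefore fair to say that no other mask practice is described, not that none takes place.

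A reader might infer that baseline VO2 is inflated and that the trial will show a false benefit. The documents do not support this. They contain no evidence on the size of any unease, and Step 1 shows that the bias runs against benefit if net VO2 is used. Nor does the text say when within the three minutes a child becomes comfortable; it states only the purpose of the period.

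It is also fair to object that a longer masked rest acts within a session, while the suspected difference is between visits. Baseline would remain the first described exposure. The ten-minute interval is also there for recovery after five gait trials, so wearing a mask and ECG through it is a small burden, in children as young as five.

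What these replies leave in place is the shared window, the lack of a control group, and an endpoint not defined as gross or net.

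**Conclusion.** The point holds as a plausible and avoidable risk, not as a demonstrated bias. Resting VO2 is taken while the child is meant to be getting used to the mask, and familiarity rises with visit number in an uncontrolled before-after study. The result may be a baseline excess that mimics benefit in gross walking VO2, to the extent that it carries into the walk, or hides benefit in net VO2, to the extent that it does not.

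Its size cannot be taken from the documents. The range of 9% to 77% is an illustration only: it rests on assumed shifts and SDs, and on the whole resting excess reaching the walk. It should not be read as this trial's error rate. The more modest cases are enough to justify a cheap change, since a spurious fall of 0.1 SD raises the chance of a false decrease from 2.5% to 5.5%, and one of 0.2 SD raises it to 10.8%.

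**What to change.** Amend Section 2.3 so that, at baseline, 4 weeks and 12 weeks alike:

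- the mask and ECG go on at the start of the ten-minute rest that is already scheduled before the 6MWT;
- resting heart rate and VO2 are taken only from the last three minutes of that rest;
- the 6MWT starts directly afterwards.

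In Section 2.2, state whether the VO2 endpoint is gross or net of rest. It would also help to record whether a child has worn the mask before baseline, for instance at screening.

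The cost is a few sentences, with no added visit, staff or test. Masked time before the walk rises from three to ten minutes, about seven more per visit. The total pause between gait analysis and the walk would be ten minutes rather than 10 + 3 = 13, which still meets the stated minimum and can be lengthened if needed.

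The change keeps the resting value out of the first masked minutes and lengthens acclimatisation before the walk. It should reduce a first-visit effect but may not remove it, so habituation should still be listed as a limitation when the change in VO2 is interpreted.

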## 1. INTRODUCTION

Cerebral palsy (CP) is a movement and postural disorder due to lesion to immature brain. Spasticity is the most common movement disorder in children with cerebral palsy (CDC) and causes difficulty with walking, musculoskeletal complications such as hip dislocation, scoliosis and joint contracture, pain and balance issues (Balaban et al., 2012). Spastic muscles are stiff and weak (Campbell & Ball, 1978). A combination of spasticity and weakness in children with CP makes them walk difficult and less efficient. Spasticity management has been very important for children with CP for activity of daily living including walking (Massin & Allington, n.d.) Using botulinum toxin A (BoNT-A) injections to control spastic lower limbs became almost first line treatment for children with CP to improve gait, range of motion and quality of life. (Ade-Hall & Moore, 2000). Several studies reported that children with CP showed higher energy expenditure during walking compared to typically developing peers. (Balaban 2007 & Rose et al 1990 Steele K et al 2017) This increase is due to combination of the mechanical inefficiencies during ambulation caused by spasticity (Reddihough et al., 2002), muscle co-contraction ((Balaban et al., 2012), limited range of motion, muscle weakness and loss of balance (Norman, 2004). Perhaps, improving coordination of walking by reducing in spasticity with BoNT-A may improve energy expenditure by improving coordination of muscle activity which is related to peak power output (Wakeling et al, 2010). Energy expenditure is an objective measure of evaluating the energy cost required for movement (Rose et al., n.d.) Generally, the oxygen consumption (VO2) is used to measure energy expenditure and one of the most significant markers of aerobic fitness and endurance (*ACSM's Advanced Exercise Physiology*, 2006). The rate of oxygen consumption (mL/kg/min) was significantly higher in the children with diplegia than in those with hemiplegia or with spina bifida or the healthy children (Rose et al., n.d.). Oxygen cost (mL/kg/m) was significantly higher, and velocity was significantly slower in all the groups with disability than in the healthy children (Duffy and Graham 2014). Balaban et al showed that botulinum toxin A injections to spastic gastric muscles decreased VO2 and gait parameters at 2-month post injections. We hypothesized that BoNT-A injections to spastic lower limbs of ambulant spastic CP decrease energy expenditure during walking. The aim of this study is to investigate the effect of spasticity management using Dysport® (AbobotulinumtoxinA) on the walking efficiency, oxygen consumption and gross motor function and gait parameters of children with CP.

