
## 2. DESIGN

This study is a single center, open label study.

We seek to recruit 15 children diagnosed with Cerebral Palsy (CP) in order to determine the efficacy of single event multi level chemoneurolysis (SEMLC) with Dysport® on energy expenditure as measured by oxygen consumption (VO2) during the 6 minute walk test.

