#### (4 Weeks Post Treatment)

All procedures during the 4 weeks post treatment will mimic those conducted during the baseline visit (i.e., Modified Ashworth Scale, Modified Tardieu Scale, range of motion, CP QOL, gait analysis, 6MWT with oxygen consumption).

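### The resting VO2 measured before each walk has no analytic use, so in this single-arm study a fall in resting VO2 alone could be reported as lower energy expenditure of walking.

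*Combined protocol and SAP*

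**What the plan says.** The Introduction hypothesises that the injections "decrease energy expenditure during walking". Section 2 (Design) takes energy expenditure to be VO2 "during the 6 minute walk test". The primary question in Section 2.2 concerns "energy expenditure and walking efficiency as measured by oxygen consumption (VO2) and gait parameters during the 6 minute walk test", and its hypothesis is that "energy expenditure (VO2) will decrease due to increased walking efficiency and gait parameters during the 6 minute walk test".

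Section 2.3 says that oxygen consumption "will be determined while the participant performs the 6MWT". Before the walk, with the mask on, "a three minute rest period will be given while resting heart rate (HR) and oxygen consumption" are measured. The reason given for this rest period is "In order for the child to become comfortable with the face mask". For week 4, "All procedures during the 4 weeks post treatment will mimic those conducted during the baseline visit"; the week 12 text says the same in substance. Resting VO2 is therefore repeated at both follow-up visits by implication.

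No section subtracts resting VO2, adjusts for it, or sets it beside walking VO2. The words gross and net do not appear, and the primary VO2 has no stated unit or averaging window. The text available for review has no statistical analysis section that could supply these.

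**The concern.** The hypothesis is about walking. VO2 recorded during a walk has two parts: what the child would use at rest, and what walking adds. Only a fall in the second part supports the hypothesis, yet a fall in either part lowers the outcome as written.

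Section 2.3 itself suggests one way in which the resting part might shift. The rest period exists to accustom the child to the mask, and children aged 5–17 may be less uneasy with it at the second and third visits. If that unease also raises VO2 during the first walk, VO2 will fall at follow-up whatever the treatment does. The study has one open-label arm, so no control group would reveal such a shift. The resting value taken at the same visit is one of the few internal checks available, and the plan gives it no use. At stake is a possible false claim of benefit on the primary outcome.

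**Working it through.** The plan gives no VO2 value, SD, significance level or effect size, so it has no figure of its own to reproduce. What follows shows the possible size under stated assumptions.

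**Inputs**
- n = 15, one arm (Section 2).
- Assumed: resting VO2 (R) 4–6 mL/kg/min, walking VO2 (W) 14–20 mL/kg/min, resting fall (f) 10–20%.
- Assumed for the significance check: paired t-test, two-sided 5% level, SD of within-child change 1–3 mL/kg/min.

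**Step 1. Share of walking VO2 that is rest** = R / W
- Lowest: 4/20 = 20%.
- Middle: 5/16 = 31%.
- Highest: 6/14 = 43%.

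**Step 2. Fall in walking VO2 when only rest falls** = R × f / W. Net VO2 (W − R) is held constant.

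| R | W | f | Fall, mL/kg/min | Fall, % of W | Change in net |
|---|---|---|---|---|---|
| 4 | 20 | 10% | 0.4 | 2.0% | 0 |
| 5 | 16 | 10% | 0.5 | 3.1% | 0 |
| 5 | 16 | 20% | 1.0 | 6.25% | 0 |
| 6 | 14 | 20% | 1.2 | 8.6% | 0 |

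**Step 3. Chance that a resting-only fall is significant in gross VO2** (noncentral t, n = 15, counting significance in the direction of a fall). The two falls are those of the middle rows of Step 2.

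| Mean fall | SD 1 | SD 2 | SD 3 |
|---|---|---|---|
| 0.5 | 0.44 | 0.15 | 0.09 |
| 1.0 | 0.95 | 0.44 | 0.23 |

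The effect runs from negligible to decisive, and the documents do not settle where it lies.

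**Step 4. What subtraction does not correct**
- *Proportional calibration drift.* With a 10% gain error, R goes from 5 to 4.5 and W from 16 to 14.4. Net goes from 11 to 9.9, which is also −10%. Net VO2 does not reveal the error.
- *Unease confined to the rest period.* Suppose baseline rest reads 5.5 instead of 5.0, and the walk is unaffected at 16. At follow-up, rest reads 5.0 and walking VO2 has truly fallen by 0.5 to 15.5. Measured net is 16 − 5.5 = 10.5 at baseline and 15.5 − 5.0 = 10.5 at follow-up. The true net fall of 0.5 (11 to 10.5) disappears.

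The second case gives the same pattern as a resting-only shift: gross falls, rest falls by the same amount, and net is flat. Net VO2 can therefore qualify a gross result but cannot overrule it.

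**The case against.** **The plan never says gross.** This stands. A reader might infer that the sponsor deliberately chose gross VO2 and that a resting fall would certainly be misreported. The documents support neither. Uncorrected VO2 is the plain reading, because the value is taken during the walk and no subtraction is described, but the choice is not stated. The misreading is something that could happen.

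**The size is entirely assumed.** This also stands. The 8.6% end needs the highest rest, the lowest walking VO2 and the largest fall together.

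**Conditions are already partly standardised.** Section 2.3 requires at least ten minutes of rest between measures, then three minutes masked, with the procedures repeated at follow-up. This makes a shift less likely but does not remove growing familiarity with the mask.

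**Gross VO2 need not understate benefit.** A reader might infer that it does, because a true 10% fall in net VO2 appears as 10% × (W − R)/W, or 5.7% at 6 and 14 and 8.0% at 4 and 20. That holds only if percentage change is analysed, which the plan does not say. For change in mL/kg/min with rest constant, gross and net changes are identical.

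**Net VO2 should not be a gatekeeper.** It is tempting to require a fall in net VO2 before any benefit is claimed. The second case in Step 4 shows that this could discard a real effect, and a bare requirement to fall would be undefined with 15 children.

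**Walking speed is a separate problem.** Pace is self-selected, and Section 2.2 expects distance to increase. A child who simply walks more slowly would lower both gross and net VO2 per minute. This is true and limits what the fix can achieve, but it does not remove the resting-VO2 gap.

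**Conclusion.** The concern holds in a limited form. Resting VO2 is measured at every visit and has no analytic use, while the primary hypothesis attributes a fall in VO2 during the walk to walking efficiency. On the plain reading that this VO2 is uncorrected, a resting shift would pass one-for-one into the primary outcome, with no control group to expose it.

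Under the assumed ranges the resulting fall is 2.0–8.6% of walking VO2 with net VO2 unchanged. The documents neither confirm nor exclude any value in that range, and they do not show that resting VO2 will fall. The point deserves action because the remedy uses data already collected. Confidence is medium.

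**What to change.** 1. State in Section 2.2 that the primary VO2 is the uncorrected value during the walk.
2. For each child and visit, also compute net VO2: walking VO2 minus that visit's resting VO2. Fix in advance which part of the three minutes counts as rest, since the same period serves for getting used to the mask.
3. Report paired changes from baseline in resting, gross and net VO2 side by side, with 95% intervals, at 4 and 12 weeks.
4. Add a limit on attribution: if gross VO2 falls while resting VO2 falls by a similar amount and net VO2 shows little change, the fall is not attributed to walking efficiency without noting that it may reflect resting VO2.
5. State the limits of net VO2: it is noisier, it may be biased against benefit if mask unease inflates baseline rest, and it does not correct proportional calibration drift or a change in walking speed.

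The cost is wording and a few extra rows in one results table. No visit, measurement or burden on the children is added. Net VO2 carries the noise of a short resting reading, which is why it supports the primary measure and does not replace it.
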